## STUDY PROTOCOL

**Type of Study:** Observational longitudinal prospective. The study has approved by etic comity of clinical research of Hospital 12 de octubre de madrid.

**Target population:** Pediatric population undergoing surgery intervention in 12 de octubre hospital.

**Sample:** A convenience sampling will be carried out among the patients undergoing surgical intervention according eligibility criteria.

- **Inclusion criteria:** Children with age from 4 years to 18 years. Undergoing surgery for any surgical specialty. ASA Status (American Society of Anesthesiologist) from I to III.
- **Exclusion Criteria:** Children who do not understand and speak Spanish correctly. Children with verbal communication problems.
- **Stratification of the sample:** The sample will be divided into 2 sample groups: a) children into 4 to 8 years, and b) children into 8 to 18 years.
- **Sample size:** To assess the degree of association between the different clinical variables and the development of chronic postsurgical pain in the pediatric population, the calculation of the sample size was based on previous literature that proposes 20 cases per variable in order to estimate a prediction model in a relatively stable manner. Therefore, taking into account that a total of 13 predictor variables were used (anxiety, catastrophism, fear of pain, fear of movement, pain interference, disability, limitation of activities, prediction of chronic pain in children and

catastrophism, anxiety, fear of pain, fear of movement of parents / guardians / companions), it was considered necessary to include at least 260 children undergoing surgery to meet the objective of this study

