### **Study design.**

- On the day of admission to the pediatric surgery service of the hospital, the potential participant and parents of the study in progress will be informed. First, patients and parents will be informed about the possibility of voluntary participation in the study. Next, the objective, process and potential benefits of this will be reported. The consent of the legal guardians will then be requested. They will be asked to fill in the information of the demographic and clinical variables, answering the self-assessment instruments (the data collection will have an estimated time of 30 'per subject), both children and parents / companions. After the surgical intervention and within a period comprised in the first 5 days, an evaluation of the dependent variables (intensity, location and distribution of pain) will be carried out in both children and parents. They should fill in the self-assessment instruments in the same way as in the pre-surgery session (this will take approximately 10 minutes).
- At 10 days, 3 months, 6 months and 12 months after the intervention, will contact the patients and relatives by telephone, and they will be asked to reply again to the evaluation of all the variables. The evaluation will be carried out by telephone interview.
- The information sheet, the informed consent, and the evaluation instruments will be collected by a researcher, stored and guarded in the Department of Radiology, Rehabilitation and Physiotherapy of the Complutense University of Madrid. Thus, complying with the provisions of Organic Law 3/2018, of December 5, on the Protection of Personal Data and guarantee of digital rights.

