CHRONIC POSTSURGICAL PEDIATRIC PAIN.

TITLE: RISK FACTORS TO DEVELOP CHRONIC POSTSURGICAL PEDIATRIC PAIN

INVESTIGATOR PRINCIPAL: [name]

PROJECT ENTITIES: COMPLUTENSE UNIVERSITY OF MADRID & 12 OCTUBRE PEDIATRIC HOSPITAL.

NUMBER OF IDENTIFICATION: 26/618

DATE: 15TH December 2020.

Statistical Analysis Plan

The results will be analyzed with the SPSS 25 statistical program (SPSS, Inc., Chicago, IL, USA). The interpretation of the statistical tests will be carried out based on a significance level of 5% ($P < 0.05$). First, the demographic variables of the sample will be presented as mean \pm standard deviation (SD), in the case of quantitative variables, and as an absolute value (relative frequency percentage in the case of qualitative variables).

The correlation of the risk factors of both children and parents with chronic postsurgical pain in children will be analyzed. To do this, the Pearson Correlation Coefficient will be used, categorizing the magnitude of the correlation as follows: strong (> 0.60), moderate (0.30-0.60), and weak or very weak (< 0.30).

Additionally, a multiple linear regression model will be used to determine the degree of association between risk factors and chronic postsurgical pain. Specifically, the intensity and location of pain will be included as criterion variables, while catastrophizing, anxiety, fear of pain, fear of movement and quality of life will be considered as predictor variables. The degree of multicollinearity existing between the predictor variables will be evaluated using the Variance Inflation Factor (VIF). The strength of association will be examined using the adjusted coefficient of determination (adjusted R^2). In addition, the regression coefficient (B), the P -value and the standardized beta coefficient (β) will be calculated for each predictor variable of the reduced final model. Thus, it will be possible to determine the variables that most directly influence the regression model.

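### Optional, low-cost improvement: the sample is justified by the stability of a prediction model, but the SAP reports only adjusted R² for a reduced model on the same children and plans no internal check

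*SAP*

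**What the plan says.** The protocol's sample-size paragraph (Study Protocol) opens with an association aim: "To assess the degree of association between the different clinical variables and the development of chronic postsurgical pain in the pediatric population". It then justifies the number by a rule of "20 cases per variable in order to estimate a prediction model in a relatively stable manner". It says that "a total of 13 predictor variables were used" and concludes that "it was considered necessary to include at least 260 children undergoing surgery".

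The SAP's regression paragraph also gives association as the purpose of the multiple linear regression. It names five predictor constructs, checks collinearity by VIF, and states: "The strength of association will be examined using the adjusted coefficient of determination (adjusted R^2". B, P and standardized beta are to be given "for each predictor variable of the reduced final model". How the model is reduced is not stated.

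Neither document mentions a bootstrap, cross-validation, hold-out sample, shrinkage or calibration.

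**The concern.** Prediction and stability are the protocol's own grounds for 260 children, yet nothing in the analysis measures either. The single strength figure comes from the children on whom the model is both reduced and fitted. Two things are missing from it:

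- Adjusted R² is penalised only for the predictors that remain, not for those tried and dropped.
- It targets the variance explained at the best coefficients, not at the coefficients actually estimated. A fitted model applied to other children does worse than that.

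If the report goes on to say how well risk factors predict later pain in other children, the adjusted R² will on average be too favourable for that statement. The reader will also be unable to tell whether another sample would have kept the same predictors.

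**Working it through.** **The plan's own figure.** 20 cases × 13 predictors = 260, which reproduces. The bracketed list names 12 predictors (8 child, 4 parent), and 20 × 12 = 240; that is a separate matter. The SAP names 5 constructs, or 9 if the four shared ones are counted for child and parent and quality of life is added. The candidate count is therefore shown over 5 to 13.

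**Inputs.** From the documents: n = 260, the 5% level, adjusted R² and a reduced model. Assumed: complete data, normal outcome and predictors, scales mutually correlated 0.4, 3 true predictors, true R² of 0.05 to 0.20, and backward elimination at P<0.05.

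**Formulas** (outcome variance 1, predictor correlation matrix C, true coefficients β, k predictors kept):

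- Adjusted R² = 1 − (1 − R²)(n − 1)/(n − k − 1).
- R² in new children = 1 − [(1 − true R²) + (b − β)′C(b − β) + a²], where b are the fitted coefficients (0 if dropped) and a is the fitted intercept.

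**Step 1: no reduction.** For normal predictors, the full model's expected R² in new children is 1 − (1 − true R²)(n + 1)(n − 2)/[n(n − p − 2)]. With true R² 0.10:

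- 12 candidates: (261 × 258)/(260 × 246) = 1.0528, and 1 − 0.9 × 1.0528 = 0.052. Simulation gave adjusted R² 0.100 against 0.052, a gap of 0.048.
- 5 candidates: (261 × 258)/(260 × 253) = 1.0237, and 1 − 0.9 × 1.0237 = 0.079, a gap of about 0.02. Simulation gave 0.022.

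Adjusted R² is on target for the association with the full candidate set (0.100 against 0.10). The gap to new children is there before any predictor is dropped.

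**Step 2: with reduction.** Means over 1,500 simulated datasets of 260:

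| Candidates | True R² | Adjusted R², reduced model | R² in new children | Gap |
|---|---|---|---|---|
| 12 | 0.05 | 0.058 | 0.013 | 0.045 |
| 12 | 0.10 | 0.105 | 0.060 | 0.045 |
| 12 | 0.20 | 0.205 | 0.169 | 0.036 |
| 9 | 0.10 | 0.103 | 0.064 | 0.039 |
| 5 | 0.10 | 0.099 | 0.070 | 0.029 |

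A repeat run at true R² 0.10 gave 0.106 against 0.061 (12 candidates) and 0.101 against 0.070 (5). The population R² of the predictors kept was about 0.08. Adjusted R² therefore exceeds it by 0.101 − 0.08 ≈ 0.02 to 0.106 − 0.08 ≈ 0.03.

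**Step 3: sensitivity.** With 13 candidates, 4 true predictors and correlation 0.3, the means were 0.105 against 0.054 at true R² 0.10 and 0.503 against 0.485 at 0.50. The gap falls from about 0.05 to about 0.02.

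- *Attrition.* Contacts run "At 10 days, 3 months, 6 months and 12 months after the intervention" and the sample size has no dropout allowance. With an assumed 20% loss (n = 208), 12 candidates and true R² 0.10, the result is 0.106 against 0.052, a gap of 0.054.
- *Age groups.* The protocol says "The sample will be divided into 2 sample groups". If models were fitted separately in an assumed equal split (n = 130, 13 candidates, true R² 0.10), the result is 0.117 against 0.016, a gap of 0.101.

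**Step 4: scale and stability.** One study's adjusted R² has a standard deviation of about 0.037 at true R² 0.10, against gaps of 0.029 to 0.045. The excess is an average: with 12 candidates, adjusted R² was above the new-sample value in 75% to 91% of datasets (true R² 0.20 to 0.05). At true R² 0.10, two samples of 260 kept the same predictors about 5% of the time with 12 candidates and 14% with 5.

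**Step 5: does the remedy work?** At true R² 0.10, bootstrap-corrected R² averaged 0.054 to 0.057 against a new-sample value of 0.064 (60 datasets × 100 resamples per setting, a small test).

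**The case against.** A reader might infer that the reported strength is wrong, or that it overstates what the study claims. The documents do not support that. Both give association as the aim, the SAP labels adjusted R² a strength of association, and prediction is mentioned once, to justify the sample size. No score, individual forecast or use in other children is planned. Against the full candidate set's population R², adjusted R² is almost exactly right: 0.105 for 0.10 and 0.205 for 0.20. Making a corrected figure of about 0.055 the sole headline would change the estimand and understate that association by nearly half. All of this stands.

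It is also fair that reduction is not the main source of the gap to new children. With 12 candidates at true R² 0.10 the gap is 0.048 without reduction and 0.045 with it; with 5, reduction adds about 0.01. The words about a reduced model follow the VIF sentence, so the reduction could be for collinearity alone, without using the outcome. The selection effect would then disappear, though the gap from estimating coefficients would remain.

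One part of the objection does not stand. The excess is not confined to prediction: if predictors are dropped using the outcome, the reduced model's adjusted R² also exceeds the population association of the predictors it keeps (0.101 to 0.106 against about 0.08).

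**Conclusion.** The point holds as a cheap improvement, not as a mistake in the plan. The protocol relies on the stability of a prediction model, and the SAP plans nothing that would show it.

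At n = 260 and true R² 0.10, adjusted R² exceeds on average the population R² of the retained predictors by about 0.02 to 0.03. It exceeds the fitted model's R² in new children by about 0.03 (5 candidates) to 0.045 (12 candidates). These are modest amounts in absolute terms, similar to or below one study's sampling error. In relative terms they matter when R² is low (0.105/0.060 = 1.75 with 12 candidates). They shrink as R² rises and grow with attrition or separate age-group models, which neither document says will be fitted.

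The direction held in every setting tried. The sizes rest on the assumed true R², scale correlation, number of true predictors and elimination rule, none of which the documents give. The figures do not show that 260 children are too few, or that adjusted R² fails at the job the SAP gives it.

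**What to change.** In the SAP's regression paragraph:

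1. State the reduction rule, including whether it uses the outcome. A bootstrap cannot be specified without it.
2. Keep adjusted R² and label it the apparent strength of association.
3. Report beside it a bootstrap optimism-corrected R² (for example 500 resamples, repeating the full reduction in each), and from the same resamples the calibration slope and how often each predictor is retained.
4. Base any statement about predicting pain in other children on the corrected figure. Otherwise, limit the conclusions to association.

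The cost is some SAP wording and a short script, possibly outside the SPSS regression menu, with no new data or patients. The corrected R² will look less favourable and, on the small test above, slightly undershoots the new-sample value.

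### The SAP judges influence from a reduced model with no stated reduction rule, and promises no adjusted estimate for a factor that is dropped

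*SAP*

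**What the plan says.** The regression paragraph of the SAP names five constructs: "catastrophizing, anxiety, fear of pain, fear of movement and quality of life will be considered as predictor variables". It says collinearity will be assessed by the variance inflation factor (VIF), with no cut-off and no action attached, and that adjusted R² will describe strength of association. B, P and beta "will be calculated for each predictor variable of the reduced final model". The use made of them follows directly: "Thus, it will be possible to determine the variables that most directly influence the regression model".

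The only other per-factor analysis comes earlier in the SAP: "The correlation of the risk factors of both children and parents with chronic postsurgical pain in children will be analyzed", by Pearson coefficient and without adjustment. The 5% level is given for interpreting tests, not for entering or removing predictors.

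The Protocol adds no modelling text. Its Sample size item relies on literature that "proposes 20 cases per variable in order to estimate a prediction model in a relatively stable manner", "taking into account that a total of 13 predictor variables were used", and arrives at 260 children.

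**The concern.** The study asks which factors are associated with chronic postsurgical pain, and the SAP answers from whatever survives an undescribed reduction. Two things are at stake.

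First, a dropped factor has no promised adjusted estimate. A reader cannot tell whether an independent association is ruled out or merely uncertain.

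Second, if predictors are dropped because of their relation to pain, the survivors are partly chosen for having large estimates. Their B values are then biased away from zero when true effects are weak, and their P-values take no account of the choice.

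With no rule written down, the rule can also be picked after the data are seen.

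**Working it through.** **Inputs from the documents.** At least 260 children, 20 cases per variable and 13 predictors (Protocol, Sample size); five constructs (SAP). Nine predictors is an inference: four psychological constructs for child and parent plus quality of life, 4 × 2 + 1 = 9.

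**Plan's own figure.** 20 × 13 = 260, which reproduces. Cases per variable are 260/13 = 20, or 260/5 = 52 with the five constructs.

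**Assumptions, not in the documents.** Gaussian data with residual SD 1; equal correlation r between predictors; three equal true effects b of the same sign (in residual SDs of pain per SD of predictor); backward removal at P > 0.05; k = 5, 9 or 13 candidates; n = 260; 3,000 simulated studies per setting.

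**Step 1: can the Pearson correlation replace an adjusted estimate?** For a factor with no independent effect, its correlation with pain is 3br / √(1 + b²(3 + 6r)). At r = 0.4:
- b = 0.12: 0.144/√1.0778 = 0.139
- b = 0.20: 0.240/√1.216 = 0.218
- b = 0.30: 0.360/√1.486 = 0.295

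Among dropped factors with no independent effect, the Pearson test is significant in about 60%, 96% and over 99% respectively. Among dropped factors with a true effect it is significant in 86%, over 99% and 100%. At b = 0.12 the first figure falls to 17% at r = 0.2 and rises to 93% at r = 0.6. The correlation does not separate the two kinds of dropped factor well.

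**Step 2: retained true effects under outcome-based removal** (r = 0.4 unless stated)

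| Setting | Mean estimate / truth | 95% interval coverage |
|---|---|---|
| b = 0.12, removal at 0.05, k = 5/9/13 | 1.69/1.70/1.69 | 83.1/83.6/84.7% |
| b = 0.12, removal at 0.10 to 0.157 | 1.44–1.55 | 89–92% |
| b = 0.12, one true effect, removal at 0.05 | 1.47–1.57 | 88–93% |
| b = 0.12, five true effects, removal at 0.05 | 1.76 | 81.7% |
| b = 0.12, r = 0.2, removal at 0.05, k = 5/13 | 1.53/1.52 | 91.0/91.2% |
| b = 0.12, r = 0.6, removal at 0.05, k = 5/13 | 2.00/1.97 | 62.9/70.7% |
| b = 0.20, removal at 0.05 | 1.18–1.19 | 93.5–93.7% |
| b = 0.30, removal at 0.05 | 1.01 | 95.4–95.9% |

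**Step 3: the full model at b = 0.12, r = 0.4, k = 5/9/13.** Over all rows, the mean estimate is 1.00 times the truth and coverage is 95.1/94.9/95.2%. Over rows with P < 0.05 only, the figures are 1.64/1.70/1.72 times and 92.8/92.2/92.7%. True effects are non-significant in 64.1/65.4/68.2% of cases, against 51.0/53.6/56.3% dropped by backward removal.

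**Step 4: price in precision.** The ratio of full-model to reduced-model standard errors for retained variables is 1.12–1.16 at b = 0.12, 1.06–1.12 at 0.20 and 1.05–1.10 at 0.30. At r = 0.6 and b = 0.12 it is 1.26–1.27.

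**Step 5: removal on VIF instead.** With equal correlation, VIF = (1 + (k − 2)r) / ((1 − r)(1 + (k − 1)r)). At r = 0.4 this is 2.2/1.56 = 1.41 for k = 5 and 5.4/3.48 = 1.55 for k = 13. The largest simulated sample VIF was 2.41 at r = 0.4 and 3.75 at r = 0.6. Cut-offs of 5 or 10 would remove nothing in these settings. VIF does not involve pain, so removal on it alone does not select on the outcome.

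**The case against.** Several points against the concern stand and limit it.

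- **No interval is promised.** The SAP lists B, P and beta. A reader might infer that its published intervals would be too narrow, but it plans none. The coverage figures describe intervals that a reader would build from the reduced model.
- **Like for like, the inflation is similar.** If only significant rows of the full model are read, exaggeration is about the same as after backward removal. Much of it comes from low power combined with reading significant rows. The matched coverage gap is about 8 to 10 points at removal 0.05, not the full distance from 95%.
- **The removal rule is assumed.** A reader might infer stepwise testing at 5%. No such method is named, and the 5% level is tied only to interpretation. Looser thresholds or a single true effect reduce the harm; five true effects or higher correlation increase it.
- **Reduction may be by VIF**, the only predictor check named. There is then no selection bias to report.
- **A full-model table is not ruled out.** The team may still publish one. The point is that the plan does not commit to it.
- **Affordability is tight.** Twenty cases per variable with 13 predictors needs complete data on all 260 children, who are followed by telephone: "At 10 days, 3 months, 6 months and 12 months after the intervention". One missing child gives 259/13 = 19.9. Two equal age groups modelled separately give 130/13 = 10, or 130/5 = 26 with five constructs.

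None of this supplies the missing rule or an adjusted estimate for a dropped factor.

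**Conclusion.** The gap is real and modest. On the text alone, influence is judged from a model whose derivation is unstated, and a dropped factor is left with an unadjusted correlation. That holds whichever reduction rule is used.

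The further harm is conditional. It requires removal based on the relation to pain and true effects near 0.12 SD. With one to three true effects, r = 0.4 and thresholds from 0.05 to 0.157, retained estimates are then about 1.5 to 1.7 times the truth, and constructed intervals cover about 83 to 93%. It is worse at r = 0.6, small at 0.20 SD and negligible at 0.30 SD.

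Two stronger conclusions are tempting: that the planned P-values are necessarily invalid, and that a full model would find more true factors. The first needs a selection method that the documents do not state. The second is contradicted by Step 3. The full model's gain is an unselected adjusted estimate with a valid interval for every factor.

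**What to change.** In the SAP:

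1. Fix the predictor list. The SAP's five constructs and the Protocol's list differ: quality of life appears only in the SAP, and the Protocol states 13 predictors but names 12.
2. Make the full model with that list the inferential result for pain intensity. Report B with 95% CI, beta and P for every predictor, and the full model's adjusted R².
3. Judge influence from the whole table, not from its significant rows.
4. If a reduced model is also shown, state its removal rule or VIF cut-off, list what was dropped, and label it exploratory.

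Whether a linear model suits pain location, and which follow-up is modelled, are separate questions.

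The cost is SAP wording and a longer table, with no new patients or data. The statistical price is standard errors about 5 to 16% larger at r = 0.4 and about 26% larger at r = 0.6. If data are incomplete or the age groups are modelled separately, a 13-predictor model falls below the Protocol's own ratio; the five-construct model has more room.

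### The SAP infers which variables matter most from B, P and standardized beta, but plans no interval or between-coefficient comparison that could support an ordering

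*SAP*

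**What the plan says.** The SAP fits a multiple linear regression with intensity and location of pain as criterion variables, and "catastrophizing, anxiety, fear of pain, fear of movement and quality of life will be considered as predictor variables". It checks overlap between predictors with the VIF, without a threshold or a consequence. Fit is judged by adjusted R2. For each predictor it then plans B and the P-value, and "the standardized beta coefficient (β) will be calculated for each predictor variable of the reduced final model". The plan ends with the inference: "Thus, it will be possible to determine the variables that most directly influence the regression model".

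No confidence interval, standard error, bootstrap or test between coefficients appears in either document.

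The Protocol's sample-size paragraph relies on literature that "proposes 20 cases per variable in order to estimate a prediction model in a relatively stable manner". It continues, "taking into account that a total of 13 predictor variables were used", and concludes that "it was considered necessary to include at least 260 children undergoing surgery".

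**The concern.** Saying that some variables influence a model most is a statement about differences between coefficients. The planned outputs do not measure those differences. A small P-value for one predictor beside a large one for another does not show that the two coefficients differ. A standardized beta also depends on the spread of each scale in this convenience sample and on which correlated scales share the model. The VIF shows how much that overlap inflates a variance, but not how far apart two coefficients must lie before their order can be trusted.

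The sizing rule does not fill the gap. Twenty cases per variable is offered as a basis for a reasonably stable prediction model, not for separating or ordering coefficients.

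At stake is the comparative part of the report. In a study of risk factors, readers will want to know which factors stand out, and they would have no means to judge whether the first differs from the second.

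**Working it through.** **The plan's own figure.** 20 × 13 = 260, which reproduces. The list that follows names 8 child and 4 parent or companion items, 12 in all (20 × 12 = 240). The SAP names 5 constructs and does not say whether child and parent versions both enter; if they do, there could be up to 10. The check therefore uses five predictors, with 12 as a sensitivity case.

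**Inputs.** n = 260 (Protocol). Assumed, because the documents give none: a continuous outcome such as pain intensity; common pairwise correlation r = 0.3, 0.5 or 0.7; one leading true beta, with three others at 0.05 and one at 0.025; two-sided 95% intervals.

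**Precision of a difference.** With p equally correlated standardized predictors:

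- R2 = (1 − r)Σβ² + r(Σβ)²
- 95% half-width of β1 − β2 = 1.96 × √[2(1 − R2) / ((1 − r)(n − p − 1))]
- VIF = (1 + (p − 2)r) / [(1 − r)(1 + (p − 1)r)]

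For a leader of 0.20, Σβ = 0.375, Σβ² = 0.048125 and n − p − 1 = 254:

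| r | R2 | VIF | Half-width of difference | True gap to second |
|---|---|---|---|---|
| 0.3 | 0.076 | 1.23 | 0.20 | 0.15 |
| 0.5 | 0.094 | 1.67 | 0.23 | 0.15 |
| 0.7 | 0.113 | 2.72 | 0.30 | 0.15 |

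The half-width exceeds the true gap in every row.

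For a leader of 0.30, Σβ = 0.475 and Σβ² = 0.098125. R2 is 0.136 at r = 0.3 and 0.187 at r = 0.7, and the half-width is 0.19 and 0.29, against a true gap of 0.25.

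**Why P-values do not substitute.** At r = 0.5 with a leader of 0.20, the SE of one beta is √(0.906 × 1.67 / 254) = 0.077. If the estimates equal the truth, the leader has z = 0.20 / 0.077 = 2.6 and the second z = 0.05 / 0.077 = 0.65, so one is significant and the other is not. The difference has SE 0.234 / 1.96 = 0.119 and z = 0.15 / 0.119 = 1.3, which does not separate them.

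**How often the true leader shows the largest estimate** (simulation of ordinary least squares, n = 260):

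| Leader's true beta | Five predictors, r 0.3-0.7 | 12 scales |
|---|---|---|
| 0.15 | about 47-63% | about 39-52% |
| 0.20 | about 63-81% | about 59-74% |
| 0.30 | about 88-98% | about 91-98% |

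The 12-scale case uses correlations within child and within parent scales of 0.3 to 0.6 and across them of 0.2 to 0.4, with three other betas at 0.05 and eight at 0.025. The lower figure in each cell belongs to the stronger overlap.

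**Other shapes of effect.** With five betas of 0.25, 0.20, 0.15, 0.10 and 0.05, the true leader comes first in 65%, 61% and 57% of runs at r = 0.3, 0.5 and 0.7. In five-predictor runs with betas falling evenly to zero (R2 0.20 to 0.40), the interval for first against second excluded zero in only 4-18%. One dominant predictor (0.40 against 0.02) came first in at least 98% of runs, even at r = 0.7.

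**Not included.** Selection into the reduced model was not simulated, because the method is not stated; it would add instability. The Protocol gives no allowance for loss to follow-up. If 30% were lost (n = 182), five evenly falling predictors at r = 0.5 give 57-70%, against 60-76% at n = 260.

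**The case against.** The strongest reply is that the SAP does not say betas will be ranked or that a single top factor will be named. It lists three quantities and speaks of variables in the plural, so scoring only first place is stricter than the text. That is fair, and the percentages illustrate instability rather than predict an announced result. The comparative claim remains, and the planned outputs still carry no measure of its uncertainty.

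A second reply is that the effects could be larger. This also stands: a leader of 0.30 would usually be found, and a dominant one almost always. The documents do not say which case applies, and without intervals the report could not show it either.

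A third is that overlap is already addressed through the VIF. This helps only in part. In the five-predictor settings above the VIF was 1.2 to 2.7, while a leader of 0.20 missed first place in about 19-37% of studies.

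A reader might also infer a causal claim about pain. The sentence speaks of influence on the regression model, and the SAP elsewhere describes its aim as association, so the wording is loose rather than a stated causal aim. Nor do the documents say that an ordering would decide who receives attention before surgery.

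**Conclusion.** The point holds in a limited form. The SAP promises a comparative conclusion that B, P, beta and the VIF cannot support by themselves, because none of them measures the difference between two coefficients. Under moderate effects (a leader of 0.15 to 0.20), the truly strongest of five predictors has the largest estimate in roughly 47-81% of studies, and two betas need to differ by about 0.2 to 0.3 to be separated. Under a strong leader (0.30) the order at the top is right in about 88-98%.

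All these figures rest on assumed correlations and effect sizes. It would go too far to say that the study will often put the wrong factor first, since that depends on effects the documents do not give. The regression itself is not invalidated. The importance is minor to moderate: a cheap change to reporting and wording that alters what may be concluded.

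**What to change.** 1. Report B and standardized beta with 95% confidence intervals for all prespecified predictors, not only those kept in the reduced model. This requires the SAP to state which child and parent scales enter.
2. Replace the closing sentence with a statement of which factors are associated with pain.
3. Call one factor more strongly associated than another only if an interval for the difference between their standardized betas excludes zero. A bootstrap interval is suitable and should repeat any selection step.

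A relative-importance analysis (share of R2) is optional.

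The cost is some SAP wording and a bootstrap, with no new data, patients or visits. The downside is that the report may have to say that several factors cannot be separated.
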